# 14.6.1.4 Reliability of RPPM Measurements (signal to noise, dynamic range, and linearity of RPPM measurements):

- *Signal to Noise Ratio:* For a given protein target (e.g. AKT-pSer473, mTOR, etc.), we scanned the array and the spot intensity normalized relative to total protein calculated using Spyro Ruby fluorescent staining. A standard single value was generated for each sample on the array using Image Quant v5.2 software. Spot intensity was integrated over a fixed area (signal). Local background intensity was calculated for each spot with the unprinted adjacent slide background using JMP v5.0 software (noise). The limit of detection was defined as 2 standard deviations above the background while the functional sensitivity was defined as the lowest signal giving a CV% of less than or equal to 20% within an array; 10 replicates of three defined cell lines were used to estimate the coefficient of variation in the average intensity of each protein. Individual RPPM protein targets that did not fall above 2 standard deviations above background in at least one cell condition were not carried forward in our analysis of RPFNA cytology.
- **Defining the Dynamic Range and Linearity in RPPM:** We tested for the dynamic range and linearity of RPPM for key nodal signaling proteins, through (a) internal serial dilution and (b) a mixture experiment. The range of and

linearity of RPPM protein expression was compared to western analysis. Twenty replicates of a defined standard titration curve [1:0, 1:1; 1:2; 1:5; 1:9; 0:1] were arrayed on each slide. Analysis was performed by taking the mean intensity of 20 individual applications for a given concentration within a slide and comparing it to the mean intensity of the remaining six slides. Analysis of inter- and intraspot reproducibility and linearity showed good correlation (correlation coefficient r2=0.989). There was agreement for the 5 proteins tested AKT-pSer473 (r2=0.999), EGRF (r2=0.982), ERK-pThr204 (r2=0.991), MEK-pSer217 (r2=0.977), and mTor (r2=0.992). These data show strong correlation between RPPM and western analysis.

**14.6.1.5 Exploratory Biomarker:** RPFNA samples will be banked for future determination of metformin tissue levels. This endpoint will help support a direct insulinindependent mechanism. Tissue will be analyzed from the fluid associated with RPFNA using a protocol adapted from Wang *et al.*. Therefore, there will be no additional risk or discomfort to the patient. This analysis will be performed in the laboratory of as an exploratory study.

#### 14.6.2 Research Serum

- **14.6.2.1** The risk of these serum studies is the loss of about 33.5 mL of blood. The blood collected will yield approximately 10-12 mL red top serum and 4 mL SST serum.
- **14.6.2.2 Measures of Obesity:** Serum IGF and other cytokines such as IL6, IL8, MCP-1, TGFbeta, and leptin will be analyzed by ELISA. It is unclear whether the benefit from metformin is due to a direct effect on Akt/mTor or an indirect reduction on serum insulin. There is also evidence for the ability of metformin to affect IGF levels. Serum IGF as well as the other cytokines listed above will be measured by a commercially-available ELISA (ENZO kit number ADI-900150) according to manufacturer's instructions in the laboratory of Approximately 2.0 ml serum will be required for these assays.
- 14.6.2.3 Measures of Breast Cancer Risk: Serum samples will be tested for estrogen and progesterone by commercially available ELISA assays according to manufacturer's instructions (Cayman Chemical Item Numbers 582251 and 582601) in the laboratory of Approximately 500 microliters of serum will be required for this assay.
- **14.6.2.4 Exploratory Biomarker:** Serum samples will be banked for future determination of metformin levels. This endpoint will help support a direct insulin-independent mechanism.

#### 14.6.3 EDTA Whole Blood

- 14.6.3.1 The risk of these EDTA whole blood studies is the loss of about 20 mL of blood. DNA will be extracted from 10 mL and stored by the Alliance PCO. From the second 10 mL tube of whole blood, DNA will be extracted and white blood cells will be isolated from the collected blood in the laboratory of
- **14.6.3.2** White Blood Cell Complex 1: Samples will be measured from isolated white blood cell mitochondria using the protocol outlined by in Methods in Enzymology. This assay will be performed in the laboratory of

- **14.6.3.3 DNA Imprinting:** laboratory will extract DNA from the EDTA whole blood and initially analyze a portion of the DNA for the presence of imprinting using standard laboratory protocols.
- **14.6.3.4 Pharmacogenomic studies:** DNA extracted by **second studies** laboratory will be used for future risk/response assays (e.g., for genetic polymorphisms such as DNA repair proteins that may correlate with efficacy and tolerability).

#### 14.6.4 Measures of Obesity and Insulin Resistance

BMI, waist to hip ratio, fasting serum glucose, fasting serum insulin, serum HOMA, serum IGF, hemoglobin A1C, and other inflammatory cytokines (as described in 14.6.2.2) will be analyzed. It is unclear whether the benefit from metformin is due to a direct effect on Akt/mTor, indirect reduction on serum insulin, or due to an indirect reduction in weight. These measures will help to support a direct insulin-independent versus an indirect insulin-dependent mechanism. BMI and waist to hip ratio will be measured by standard clinical criteria. We plan to examine whether baseline glucose predicts metformin benefit independent of insulin or whether glucose modifies effects of insulin as a predictor of metformin benefit. We will also investigate HOMA, an empirically derived estimate of insulin sensitivity calculated from a single measure of fasting insulin and glucose that correlates well with the gold standard frequently sampled intravenous glucose tolerance test, as a predictor of metformin benefit, focusing on whether it provides additional prediction beyond insulin alone. The blood collection for fasting glucose and insulin is a mandatory part of the baseline, 6-month, and yearly evaluations. Serum fasting glucose and fasting insulin will be determined by standard clinical criteria at the participating sites.

#### 14.6.5 Residual Biospecimens

All residual specimens remaining after correlative studies are completed will be shipped to the Alliance Biorepository at Ohio State University, where they will be permanently stored at -80°C according to patient consent information, until specific analyses are identified. As protocols are developed, they will be presented for Alliance and IRB review and approval. (This collection is part of a general strategy of investigation for the majority of Alliance studies.)

#### 14.7 Return of Genetic Testing Research Results

- **14.7.1** This study will only test for low penetrance alleles that confer minimal risk. Because the results generated by the genetic testing described above are not currently anticipated to have clinical relevance to the patient or their family members and will be conducted in a research facility, the genetic results will not be disclosed to the patients or their physicians.
- **14.7.2** If, at any time, genetic results are obtained that may have clinical relevance, IRB review and approval will be sought regarding the most appropriate manner of disclosure and whether or not validation in a CLIA-certified setting will be required prior to reporting any finding. Sharing of research data with individual patients should only occur when data have been validated by multiple studies and testing has been done in CLIA-approved laboratories or in a setting where a clinical trial is available based on a CLIA laboratory validated sequencing result and the patient has consented to re-contact for additional studies.

#### **15.0 DRUG INFORMATION**

#### **15.1** Metformin hydrochloride tablets

**15.1.1 Background:** Metformin hydrochloride is an oral antihyperglycemic agent used in the management of type 2 diabetes. It lowers both basal and postprandial glucose levels in type 2 diabetes patients through several mechanisms: decreases hepatic glucose production, decreases intestinal absorption and increases peripheral glucose uptake and improves insulin sensitivity. Metformin hydrochloride is not chemically or pharmacologically related to any other classes of oral antihyperglycemic agents.

The Alliance considers this study to be IND exempt. Consistent with the FDA Guidance "IND Exemptions for Studies of Lawfully Marketed Drugs or Biological Products for the Treatment of Cancer", the Alliance is not planning to use the results of A211102 to get a new indication for metformin. Metformin has been and is currently being investigated for treatment and prevention of cancer. It is not anticipated that the toxicity profile of metformin in A211102 is different from that already known. The FDA has confirmed this study to be IND exempt (IND 122334).

- **15.1.2 Formulation:** Metformin hydrochloride tablets, containing 500 mg, 850 mg, or 1000 mg metformin hydrochloride per tablet, are manufactured and distributed by various pharmaceutical companies. The metformin hydrochloride 850 mg tablets used in this trial are available commercially from Heritage Pharmaceuticals. McKesson Clinical Research Services will use study-provided funds to purchase the metformin tablets. Each tablet also contains the inactive ingredients malto dextrin, hypromellose, magnesium stearate, polyethylene glycol, povidone, corn starch, and blackberry. The tablets will be bottled and labeled by Pharm Ops, Inc. Each bottle packaged by Pharm Ops, Inc. will contain 175 tablets.
- **15.1.3 Preparation and storage:** The tablets should be stored at a controlled room temperature, with excursions to 15-30°C (59-86°F) permitted. All tablets should be kept in a secured storage area.
- **15.1.4 Administration:** Metformin hydrochloride tablets should be taken with meals.
- **15.1.5 Pharmacokinetic information:** The time to peak serum level for the immediate release product is 2 to 3 hours. The onset of action is within days, with maximum effects up to two weeks. Metformin is negligibly bound to plasma proteins. Metformin is excreted in the urine, with 90% as unchanged drug. It does not undergo hepatic metabolism. Renal clearance is approximately 3.5 times greater than creatinine clearance, which indicates that tubular secretion is the major route of elimination. Bioavailability while fasting is 50% to 60%. Half-life elimination in plasma is 4 to 9 hours.
- **15.1.6 Potential Drug Interactions:** Concomitant use of the following agents may cause hyperglycemia: thiazides, other diuretics, corticosteroids, phenothiazines, thyroid products, estrogens, oral contraceptives, phenytoin, nicotinic acid, sympathomimetics, calcium channel blockers, and isoniazid. Metformin may interact with highly protein bound drugs (salicylates, sulfonamides, chloramphenicol, probenecid). Concurrent use of other glucose-lowering agents may cause hypoglycemia. Fluoroquinolones and antidiabetic agents have been reported to cause blood glucose changes. Beta blocking agents present a minimal risk of altering glucose control in nondiabetic individuals, although severe hypoglycemia has been reported with at least one beta blocking agent. Concurrent use of metformin is contraindicated in participants receiving intravascular iodinated contrast media due to an association with lactic acidosis and acute renal failure.

- **15.1.7 Known potential toxicities:** Metformin is considered to have a favorable safety profile in diabetes mellitus patients. In a US double-blind clinical trial for patient with type 2 diabetes, gastrointestinal symptoms such as diarrhea, nausea and vomiting, abdominal discomfort, flatulence, indigestion, and asthenia were the most common reactions to the drug. These symptoms were dose-dependent, transient, and resolved spontaneously with continued use. The drug may cause GI upset so should be taken with food. Additional adverse reactions reported in 1 to 5% of subjects were abnormal stools, hypoglycemia, myalgia, lightheadedness, dyspnea, nail disorder, rash, increased sweating, taste disorder, chest discomfort, chills, flu syndrome, flushing and palpitation. A recently published trial of patients with type 2 diabetes mellitus reported a vitamin B12 deficiency with long term treatment. Lactic acidosis is a rare, but serious, metabolic complication that can occur due to metformin accumulation during treatment. Reported incidence of lactic acidosis in patients with significant renal insufficiency.
- **15.1.8 Drug procurement:** Metformin Hydrochloride 850 mg tablets will be purchased for use in the trial. Placebo tablets that are similar in size and color will also be purchased. The metformin and placebo tablets will be bottled and labeled by Pharm Ops, Inc. The bottles will be labeled so that study participants, caregivers, and investigators are blinded to the contents.

Blinded metformin/placebo: Patient-specific supplies of metformin/placebo will be ordered by the registering institution after each patient is enrolled to the study.

Fax or email the Alliance A211102 Drug Order Form to:

Patients will need to return to the clinic to receive additional supplies of blinded drug at 3, 6, and 9 months after registration. Sites may dispense a 6 month supply. However, sites that dispense a 6 month supply will be responsible for reconciliation of all medication returns. Institutional staff will contact the Registration Office for a study medication code number. Drug orders for these additional supplies should be submitted at least one week prior to each of these visits using the Alliance A211102 Drug Order Form.

Open-label metformin: All patients will be unblinded at 12 months (see Section 6.9). All patients, except those who were randomized to placebo and who opt not to cross over to open-label metformin will receive open-label metformin. After re-registering the patient per Section 6.9, site staff will order patient-specific supplies of open-label metformin using the A211102 Drug Order Form. Orders should be placed at least 1 week prior to the patients' 12-, 15-, 18-, and 21-month visits.

#### Alliance A211102

Open-label metformin will be provided as 100 count bottles. Sites are responsible to label the bottles according to their respective state pharmacy laws. A sample label is below:

The Alliance A211102 Drug Order Form is available at the Alliance and CTSU Web sites. Outdated or remaining drug/product should be destroyed on-site per procedures in place at each institution.

#### **15.1.9 Nursing Guidelines:**

- Metformin can have numerous drug to drug interactions that can cause either hyper or hypoglycemia. Assess patient's concomitant medications (including OTC) and instruct patients not to start any new medications while on the study without checking with the study team.
- Warn patients of gastrointestinal side effects when initially starting agent, including diarrhea, nausea, abdominal discomfort, flatulence, indigestion and vomiting. Agent should be taken with food to minimize these side effects.
- There is a rare but serious risk of lactic acidosis. Instruct patients to report nausea or weakness. Patient with these symptoms should have their electrolytes checked and/or corrected under the direction of the physician.
- Drug may cause hypoglycemia. Instruct patients in the signs and symptoms of hypoglycemia and to seek medical attention if they experience these.
- Instruct patients that if they need to have any procedure (i.e. CT scan with contrast) with iodinated contrast they must discontinue metformin per institutional practice prior to the procedure and must not resume it until their creatinine level is satisfactory (per institutional practices).

#### 15.2 Placebo

A placebo tablet will be provided which will be similar in appearance to the metformin HCl 850mg tablet.

**Formulation:** Pharm Ops, Inc., Inc. will formulate and produce the placebo tablets. The tablets will contain microcrystalline cellulose and other inactive ingredients: croscarmellose sodium, colloidal silicon dioxide and magnesium stearate.

#### **16.0 STATISTICAL CONSIDERATIONS AND METHODOLOGY**

#### 16.1 Study Design

#### **16.1.1 Study Populations**

A total of 177 premenopausal women will be pre-registered, among which 96 patients with atypia (Masood Score 14-17) on RPFNA at baseline are expected to be randomized between

Metformin arm and placebo control arm. It is expected that the accrual rate will be 1 patient per month and that accrual will be completed about 8 years after study activation. The randomization will be stratified for known BRCA mutation (BRCA1 or BRCA2 mutation vs. no mutation), prior excisional biopsy (atypical epithelial hyperplasia, atypical lobular hyperplasia, flat epithelial hyperplasia vs. DCIS vs. LCIS), and baseline fasting insulin > 2x ULN vs.  $\leq 2x$  ULN.

At 12 months the women in the placebo arm will be allowed to take metformin. Based on experience from 300 women undergoing serial RPFNA at Duke, it is anticipated that approximately 40% of women who are randomized to the metformin arm will have disappearance of atypia at 12 months and 60% will have persistent atypia. The estimated drop-out rate is 5% at 6 months and 10% at 12 months. Over 98% of women with atypia will have atypia on repeat RPFNA on the non-metformin arm.

We propose to test RPFNA on both right and left breasts at, 12 and 24 months after registration/randomization for the presence or absence (Masood score  $\leq$ 13) of atypia by Masood Cytology Index Score. The RPFNA at 24 months is optional for women who continue on the placebo control arm and will not receive metformin. The outcomes collected at 24 months will be exploratory. In analysis, we will consider taking a transformation, such as logarithm, of positive variables in order to improve the normality and variance stabilization. Among the 96 randomized patients, we expect that about 10% of patients will drop out at month 12. So, the power analyses are based on N= 88 patients (44 per arm).

#### 16.2 Statistical Analysis and Power Calculation

#### 16.2.1 Primary Objective:

Test for the presence or absence of atypia in RPFNA after 12 months (24 month optional for placebo group for patients who remain on placebo arm and will not receive metformin); Metformin versus placebo control:

#### **16.2.1.1 Primary Analysis**

Multiple Masood scores from each breast will be averaged for each time point. The primary endpoint of the study is the binary outcome of atypia (Masood score  $\geq$  14). In this analysis, the sampling units will be women, so that, if a woman has atypia in one breast and no atypia in the other breast, this woman will be called atypia. Presence of atypia at month 12 will be compared between two arms using the chi-square test in univariate analysis, and regressed on group indicator, age, race, stratification factors, and baseline Masood score using logistic regression in multivariate analysis. As an exploratory analysis, we will also conduct a regression analysis including the timing of baseline RPFNA (intraoperative vs. in clinic) and the number of breasts with atypia at baseline in addition to these covariates. With 44 women per arm, the primary analysis has 90% of power to detect a difference of 90% vs. 60% of atypia between placebo and metformin arms at month 12 by a chi-square test with alpha=5%.

In order to address the worst score rule, we will repeat above analyses using the maximum, instead of average, Masood score from each breast.

#### **16.2.1.2 Exploratory Analysis**

An exploratory analysis will be conducted using the breasts as sampling units, not women, so that all eligible breasts of eligible patients will be included in data analysis. The variance of the test statistic for comparing the presence of atypia at month 12 will be estimated using the generalized estimating equation (GEE) approach to account for the possible dependency among the binary atypia observations from each patient.

#### Alliance A211102

In another exploratory analysis, we will compare the continuous Masood score between two arms. The sampling unit in this analysis will be breast. The change rate (ratio) in Masood score at month 12 from baseline will be compared between metformin group and placebo control group using two-sample t-test for univariate analysis with 2-sided alpha=5%. We will also conduct multivariate analysis to regress the month 12 Masood score on group indicator, age, race, prior excisional biopsy, and baseline Masood score.

Since the sampling unit in this analysis is breast, the Masood score observations from two breasts may be potentially correlated. In order to account for possible dependency between the data points from two breasts of each woman, the variances of t-test (in univariate analysis) and regression estimates (in multivariate analysis) will be estimated using the GEE.

It is expected that about 25% of women (n = 11) will contribute one breast and the remaining 75% of women (n = 33) will contribute samples from both breasts, so that there will be about 77 (= 11x1 + 33x2) data points (breasts) per arm in this analysis. Assuming that the intracluster correlation coefficient between two breasts is 0.3, this analysis will have 84% power to detect a difference of 0.4 times the standard deviation (SD).

Similar analyses will be conducted for 24 months data.

The women or breasts with unsatisfactory repeat RPFNAs will be considered missing at random in the analysis.

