#### 6.7 Stratification factors

The stratification factors defined below will be used at the time of patient registration:

- BRCA mutation (Yes vs. No mutation or unknown).
- Prior abnormal excisional biopsy results (Yes vs. No or unknown).
- Fasting baseline insulin: (Fasting insulin > 2x ULN vs. Fasting Insulin  $\leq 2x$  ULN)

After the patient has been registered to the study, the values of the stratification factors will be recorded. The patient then will be assigned to one of the following treatment groups using the Pocock and Simon dynamic allocation procedure which balances the marginal distributions of the stratification factors between the treatment groups:

- Metformin
- Placebo

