# 16.2.2.4 Correlate baseline RPPM values with presence of atypia at month 12 and month 24:

We will combine data set of metformin and no-metformin groups (N = 88) and use the breasts as the sampling units in this analysis. The possible dependency in observations between the left and right breasts for each woman will be adjusted using the GEE approach.

The baseline RPPM value of each protein will be correlated with Masood cytology score at month 12 using a simple linear regression method. In a multivariate analysis, Masood score at month 12 will be regressed on the baseline RPPM value of each protein, group indicator, age, race, prior excisional biopsy, and baseline Masood scores. Similar analysis will be conducted using the change rate of Masood score between baseline and month 12 in place of Masood score at month 12.

The baseline RPPM value of each protein will be correlated with presence and absence of atypia at month 12. A total of 50 proteins will be tested, so that the significance of each protein will be adjusted for multiple testing by controlling the family-wise error rate (FWER) using the permutation method. We expect that about 60% of the women will have persistent atypia at 12 months. The 50 proteins were selected from a previous study so that they are expected to have reasonable effect sizes. Assuming that each woman contributes samples from only one breast and the proteins have correlation coefficient of 0.1, the multiple testing procedure controlling the FWER at 10% level by two-sided tests will have about 90% probability to detect 15 or more proteins if 25 of the 50 proteins have an effect size of 0.8 times SD [Jung and Young, 2011]. Since about 75% of women are expected to contribute samples from both breasts to the study, the real power for this analysis will be higher.

In a multivariate analysis, presence of atypia at month 12 will be regressed on the baseline RPPM value of each protein, group indicator, age, race, prior excisional biopsy, and baseline Masood scores.

A similar analysis will be conducted to correlate baseline RPPM value of each protein with Masood score and presence/absence of atypia at month 24.

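### The exploratory month-12 Masood score model in 16.2.1.2 omits two of the three allocation factors (BRCA status and fasting insulin stratum), so its standard errors are too large if those factors are prognostic

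*Combined protocol and SAP*

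**What the plan says.** Section 6.7 lists three factors recorded at registration: BRCA mutation (yes against no or unknown), prior abnormal excisional biopsy (yes against no or unknown), and baseline fasting insulin above or not above twice the upper limit of normal. Assignment uses a dynamic procedure that "balances the marginal distributions of the stratification factors between the treatment groups".

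Section 16.2.1.1 compares month-12 atypia by a chi-square test. It adds a multivariate analysis in which atypia is "regressed on group indicator, age, race, stratification factors, and baseline Masood score using logistic regression in multivariate analysis". All three allocation factors are therefore in that model.

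Section 16.2.1.2 is headed as exploratory. It compares the continuous Masood score by breast, first with a two-sample t-test on the change ratio. It then adds a multivariate analysis to "regress the month 12 Masood score on group indicator, age, race, prior excisional biopsy, and baseline Masood score". Variances come from GEE to allow for two breasts per woman. BRCA status and fasting insulin do not appear, and the section does not say why.

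**The concern.** Minimization forces the arms to be alike on the three factors. If a factor predicts the outcome, that balance makes the arm difference less variable than it would be under simple randomization. A model containing the factor gives credit for this. A model without it leaves the factor's variation in the residual, so the reported standard error exceeds the true one. Confidence intervals are then wider than the design warrants, and the test rejects less often than its nominal level.

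At stake is the precision of one exploratory comparison, and consistency between two regressions in the same plan that treat the same allocation factors differently.

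**Working it through.** **1. Inputs.** From 16.1.1 and 16.2.1.2: 88 women (44 per arm); per arm 11 women with one breast and 33 with two, so 77 breasts; intracluster correlation 0.3; difference 0.4 SD; two-sided alpha 5%. The documents give neither the prevalence nor the prognostic strength of BRCA status or raised insulin.

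**2. The plan's own figure.** The plan gives 84% power for the breast-level comparison. With working independence, the variance of an arm mean, in SD², is (11 + 66 × 1.3)/77² = 96.8/5929 = 0.01633, an effective n of 61.3. The SE of the difference is √(2 × 0.01633) = 0.1807. Power is Φ(0.4/0.1807 − 1.96) = Φ(0.254) = 60%. The 84% is not reproduced. That is a separate question and nothing below depends on it; 60% serves only as a starting point.

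**3. Simple size of the omission.** If the two factors explain a share R² of residual variance, the short model's SE is too large by 1/√(1 − R²).

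| R² (assumed) | SE excess | Power, short model | Power, factors added |
|---|---|---|---|
| 0 | none | 60% | 60% |
| 2% | 1.0% | 60% | 61% |
| 5% | 1/√0.95 = 1.026, so 2.6% | 60% | 62% |
| 10% | 1/√0.90 = 1.054, so 5.4% | 60% | 65% |

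**4. The factors belong to women, not breasts.** Step 3 ignores that both breasts of a woman share the same value. If R² is counted on breast-level variance and the 0.3 correlation includes the factors, adding them reduces the numerator 96.8 by R² × (11 × 1² + 33 × 2²) = 143 R². At 5% the excess is √(96.8/89.65) = 1.039; at 10% it is √(96.8/82.5) = 1.083. The 3-5% is therefore the simple approximation, and 4-8% is the figure on this stricter reading.

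**5. Simulation.** Pocock-Simon allocation, 88 women, 75% bilateral, correlation 0.3, robust clustered SEs, 2,500 runs per setting. Prior biopsy and baseline score are in both models. Factor prevalences and effects are assumed. SEs and power are under a 0.4 SD difference; the last column is under no difference.

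| Effect per omitted factor, prevalence | Reported SE, omit / include | True spread, omit / include | Power, omit / include | Type I error, omit / include |
|---|---|---|---|---|
| 0, 25% | 0.181 / 0.180 | 0.178 / 0.178 | 59% / 59% | 5.1% / 4.8% |
| 0.5 SD, 10% | 0.187 / 0.181 | 0.181 / 0.179 | 56% / 59% | 4.6% / 4.8% |
| 0.5 SD, 25% | 0.193 / 0.180 | 0.182 / 0.180 | 54% / 59% | 4.2% / 5.5% |
| 0.8 SD, 25% | 0.211 / 0.181 | 0.186 / 0.181 | 47% / 60% | 3.1% / 5.0% |

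Monte Carlo error on a 5% rejection rate is √(0.05 × 0.95/2500) = 0.4 percentage points. The true spread barely moves. What grows is the reported SE, and type I error falls below nominal rather than rising.

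**The case against.** The strongest reply is that this is a covariate preference in a low-stakes model. The regression supplements a t-test within an analysis labelled exploratory. The stated power for the primary endpoint rests on an unadjusted chi-square test, so the mismatch is between two supporting regressions. This stands, and it limits the importance of the point.

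The second reply is that the loss may be negligible. For a binary factor R² = p(1 − p)d². If each factor supplied half of a 5-10% share, it would need an effect of √(0.025/0.09) = 0.53 to √(0.05/0.09) = 0.75 SD at an assumed 10% prevalence, or 0.37 to 0.52 SD at 25%. The plan powers for a treatment effect of 0.4 SD, so each factor would have to matter about as much as metformin, or more. Section 3.2.15 excludes women with HbA1c above 6.3 or treated diabetes, which may make the high-insulin stratum uncommon. This also stands: the loss is conditional and could be nil.

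A reader might extend the point to the protein models in 16.2.2.4, which use "group indicator, age, race, prior excisional biopsy, and baseline Masood scores" with each protein. The documents do not support that. The target there is the coefficient of a baseline protein, which is not randomized, so the allocation argument does not carry over. The panel in 14.6.1.3 also includes IGF/insulin proteins, so adding insulin could change what those coefficients mean.

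A reader might also argue that insulin belongs in the model because it is close to metformin's mechanism. That concerns effect modification, which a main-effect term does not address. Section 14.6.4 already plans to study insulin as a predictor of benefit.

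**Conclusion.** The point holds for the linear month-12 Masood score model in 16.2.1.2 and no further. The omission is clear from the text and unexplained. Its cost depends on whether BRCA status and insulin stratum predict the score given age, race, biopsy and baseline score. On an assumed 5-10% share of residual variance, the arm-effect SE is overstated by about 3-5% by the simple formula (4-8% if the share is counted on breast-level variance). With no prognostic value the two models are equivalent.

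A reader might infer that the short model is biased, gives false positives or weakens the primary result. None of these follows: the simulated test is conservative, and the logistic model for the primary endpoint already adjusts for all three factors. This is a minor, optional improvement.

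**What to change.** In 16.2.1.2, add BRCA status and fasting insulin stratum to the covariates of the linear month-12 Masood score model, at the levels in 6.7, or state why they are left out. Code prior biopsy at its 6.7 levels too, because 16.1.1 describes that factor differently (types of atypia, DCIS, LCIS). Leave 16.2.2.4 as it is.

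The change is SAP wording only, since all three values are recorded at registration. The statistical cost is 2 degrees of freedom. It should be judged against the 88 women, who are the independent units, and not against the 2 × 77 = 154 breasts. If a BRCA or insulin stratum holds only a few women, the robust GEE variance can be unreliable, so the SAP should say how a sparse stratum will be handled.
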